## 1.0 BACKGROUND AND RATIONALE

### 1.1 Disease Background

In developed countries, prostate cancer is the most common malignancy in men and the third leading cause of death in men [1, 2]. Despite being a common cancer, it has proven challenging to diagnose accurately both primary and metastatic lesions. There are numerous reasons for this challenge including the insensitivity of serum prostate specific antigen(PSA) in distinguishing benign from malignant disease, sampling errors in unguided biopsies of the prostate, and the multifocal nature of prostate cancer lesions within the prostate [3].

In the evaluation of primary prostate cancer, the use of multi parametric MRI (mp-MRI) has increased the detection of primary prostate cancer, but there is still a significant number of undetected lesions using this technique. A recent large study [3], which correlated pre-prostatectomy mp-MRI imaging with post prostatectomy whole mount pathology (WMP) of the resected gland, reported that less than half of all individual prostate cancer lesions were identified. These tumors were most commonly small lesions (<1 cm), multifocal lesions, lesions associated with Gleason score < 3+3, and with Prostate Imaging –Reporting and Data System (PI-RADS) v2.1 score < 4. However, some of these undetected lesions have elevated PSA and Gleason scores  $\geq 7$ , making more aggressive biologic behavior likely [3].

In addition, accurate localization of metastatic lesions outside the prostate with standard of care imaging, such as magnetic resonance imaging (MRI) and computed tomography (CT) of the pelvis, lack sensitivity as they are dependent upon size criteria and may not detect disease in smaller nodes [4]. Planar bone scintigraphy, standard of care in high-grade tumors, may also under identify small lesions and may lack specificity due to uptake in additional common benign disease [5]. For these reasons, it is desirable to pursue additional imaging with greater sensitivity and specificity for detecting primary tumors as well as staging for metastatic disease [6].

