**1.4 Rationale**

A recent case report has documented that  $^{68}\text{Ga}$  PSMA-11 PET/CT may identify a prostate primary lesion even when mp-MRI does not [13]. In addition, mp- MRI may detect only a single lesion with PI-RADS v 2.1  $\geq 4$  but prostate cancer is often multifocal [3] and with the addition of  $^{68}\text{Ga}$  PSMA-11 PET/CT, those additional prostatic lesions might be identified. Several studies have demonstrated that early dynamic PET/CT imaging immediately after injection of  $^{68}\text{Ga}$  PMSA-11 can enhance primary prostate cancer detection as tumor uptake begins rapidly after injection and before the urinary bladder begins to fill with excreted tracer [7, 14].

In addition to identifying primary prostatic lesions, it is possible that  $^{68}\text{Ga}$  PMSA-11 PET/CT may be able to detect more metastatic disease than that detected on current standard of care staging imaging for patients with elevated PI-RADS scores and PSA values.  $^{68}\text{Ga}$  PMSA-11 PET/CT is reported to be able to detect small suspicious nodes and extra prostatic lesions due to its greater sensitivity and specificity compared to a variety of other imaging modalities [4, 8, 12].

The purpose of the proposed research is to evaluate the added value of  $^{68}\text{Ga}$  PSMA-11 PET/CT in relation to detect additional primary prostate cancer lesions compared to mp-MRI in a group of patients with elevated PI-RADS scores and PSA. We propose that the addition of early dynamic  $^{68}\text{Ga}$  PMSA-11 PET/CT imaging to the more usual delayed imaging will enhance detection of primary lesions and additional lesions not detected on the mp-MRI. In addition, the dynamic imaging will allow us to evaluate the kinetics of uptake in the prostate gland. It is possible that even in the absence of focal uptake, hyperemia of the gland could indicate the presence of an occult primary.

A second purpose of this research is to examine the value of  $^{68}\text{Ga}$  PSMA-11 PET/CT in this same group of patients in detecting metastatic disease at initial staging in comparison with current standard of care imaging such as CT and MRI.

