**2.2 Secondary Objectives**

- 2.2.1 To assess whether  $^{68}\text{Ga}$  PSMA-11 PET/CT can detect additional sites of metastatic disease at staging in comparison to standard of care imaging in patients with PI-RADS v2.1 score 5 (with any PSA), or score 4 and PSA  $\geq 10$  ng/mL

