### 3.2 Exclusion Criteria

- 3.2.1 Patients who have had a prior prostatectomy or radiotherapy for prostate cancer cannot participate in the study
- 3.2.2 Patients who have had a prior biopsy for prostate cancer cannot participate in the study
- 3.2.3 Patients who have been treated for cancers other than skin cancers
- 3.2.4 Subjects may not be receiving any other investigational agents for the treatment of the cancer under study
- 3.2.5 Patients may not weigh more than the maximum weight limit for the PET/CT scanner table ( $>200\text{kg}$  or 440 lbs)

---

- 3.2.6 History of allergic reactions attributed to compounds of similar chemical or biologic composition to  $^{68}\text{Ga}$  PSMA-11 or other agents used in the study such as gadolinium-based intravenous contrast agent used during the mp-MRI
- 3.2.7 Prior TURP/BPH procedures, including steam/laser therapies.

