#### **4.5 Other Modalities or Procedures**

The initial mp-MRI of the prostate is standard of care and not part of the research protocol. Per current guidelines [18], cross sectional imaging (CT or MRI) is also considered standard of care in men with unfavorable intermediate or high risk disease.

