#### 5.4 Time and Events Table

Event	Visit 1: screening	Visit 2:  GA PSMA-11 PET/CT	Follow-up
Informed Consent	X		
Demographics	X		
Clinical history	X		
Height/weight	X	X	
Physical exam	X		
Survival/patient status			X
Review pathology records			X
 Ga PSMA-11 PET/CT		X	
Other radiologic studies (CT or MRI)	X		X
Adverse event evaluation*			X

\*Adverse event evaluation up to 24 hours post injection.

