### 7.3 Unblinding Procedures

The proposed study is not blinded.

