#### **10.3 Data Analyses**

Because of the small number of subjects, descriptive statistics will be used, such as percentage of times a focus of uptake in the prostate can be seen on the PET/CT and whether this focus corresponds to any detectable abnormality on review of mp-MRI of the prostate. To be specific, we will summarize percent of incidences when 1) PET/CT is concordant with mp-MRI, 2) uptake seen on PET/CT but normal on mp-MRI and 3) no uptake on PET/CT but abnormal seen on mp-MRI. This will be displayed in a two-by-two contingency table.

Comparison will also be made to pathologic specimens from biopsy and/or prostatectomy (as reference standard) to correlate whether abnormal foci of tracer uptake correspond to sites of tumor. The per-lesion diagnostic performance of PET/CT (sensitivity and false positives) will be reported. This will be displayed in a two-by-two contingency table.

With regard to lesions outside the prostate, comparison will be made of the results from the  $^{68}\text{Ga}$  PSMA-11 scan and possible lesions seen on conventional imaging, such as pelvic CT or MRI or bone scintigraphy. To be specific, we will summarize percent of incidences when 1) PET/CT is concordant with pelvic CT/MR/BS, 2) uptake seen on PET/CT but normal on pelvic CT/MR/BS and 3) no uptake on PET/CT but lesion seen on pelvic CT/MR/BS. This will be displayed in a two-by-two contingency table.

If possible, biopsy confirmation of sites of abnormal focal  $^{68}\text{Ga}$  PSMA-11 uptake outside the prostate gland will be obtained. If biopsy is not possible due to position or size of suspected lesion, post treatment conventional imaging will be performed and results will be compared for regression in size. The per-site diagnostic performance of PET/CT (sensitivity and false positives) will be reported. This will be displayed in a two-by-two contingency table.

Agreement between two readers in continuous measurements (mean and max SUV) will be assess by intraclass correlation coefficients (ICC) and Bland-Altman plots per area of interest. Agreement between two readers in discrete measurements (visual distinguishability of primary tumor, additional primary lesion, sites of metastasis) will be assessed by Cohen's kappa.

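### Section 10.3 sets no timing rule for the conventional imaging behind Objective 2.2.1, so scans obtained after, and possibly with knowledge of, the PET can enter the staging comparison

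*Combined protocol and SAP*

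**What the plan says.** Section 2.2 asks whether PET "can detect additional sites of metastatic disease at staging in comparison to standard of care imaging". Section 1.4 states the purpose as the value of PET "in detecting metastatic disease at initial staging in comparison with current standard of care imaging such as CT and MRI". Section 2.4 makes the second endpoint per person and comparative.

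The rules that bear on when conventional imaging happens are spread over the protocol:

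- Section 3.2.2: "Patients who have had a prior biopsy for prostate cancer cannot participate in the study". Under Section 3.1.4, biopsy or prostatectomy is scheduled at entry.
- Section 1.1: "Planar bone scintigraphy, standard of care in high-grade tumors".
- Section 4.5: "cross sectional imaging (CT or MRI) is also considered standard of care in men with unfavorable intermediate or high risk disease".
- Section 5.4: the row beginning "Other radiologic studies (CT or MRI" is marked at screening and at follow-up. Pathology review is marked at follow-up only. Bone scintigraphy has no row.
- Section 7.3: "The proposed study is not blinded".
- Section 9.0 leaves standard imaging to the treating physician.

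Section 10.3 then cross-tabulates PET against pelvic CT, MR or bone scan. Besides concordance, it lists "2) uptake seen on PET/CT but normal on pelvic CT/MR/BS and 3) no uptake on PET/CT but lesion seen on pelvic CT/MR/BS". It gives no rule on which scan counts, when it must be done, or whether it is reported without the PET result.

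**The concern.** An added-yield question needs a comparator formed without the index test. If a PET-positive node or bone site prompts a directed scan, or leads a reader to call an equivocal site positive, that man or site leaves the PET-only cell and becomes concordant. The PET-only cell is what Objective 2.2.1 is about, so conventional imaging would be credited with findings it might not have made unaided.

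Two related effects are possible. Whether a man has a conventional scan at all may depend on his PET result. In addition, Section 10.3 uses post-treatment conventional imaging to verify extraprostatic PET sites that cannot be biopsied. Without a timing rule, a scan meant as confirmation can also be counted as the comparator. Section 10.2 says the data are to support a larger study, so a distorted yield would carry forward.

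**Working it through.** The plan states no power, effect size or expected yield for this comparison, so there is no figure to reproduce. The check has two parts: the order of events, then an illustration of size.

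**Order of events**

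1. *What surely precedes registration.* Only the prostate mp-MRI (Section 3.1.2). With prior biopsy excluded and the tissue procedure still pending, grade is unknown at registration.
2. *What triggers staging imaging.* Section 1.1 ties bone scintigraphy to grade, which needs tissue. Section 4.5 ties CT/MRI to risk group and does not say whether that requires biopsy.
3. *PET and biopsy.* Their order is not fixed outright. Sections 4.3 and 10.3 seek biopsy confirmation of PET foci, and pathology review is scheduled only in follow-up. PET before tissue is the natural reading, which puts grade-triggered imaging after the PET.
4. *Who knows the PET result.* Seeking biopsy of PET foci implies that the clinical team sees it. Section 4.3 describes two independent readers for PET; no reading rule is given for conventional imaging.
5. *What the table admits.* Section 5.3 collects disease-related imaging for 2 years, and Section 10.3 sets no cut-off by PET date or start of treatment.

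The share of men whose conventional imaging follows the PET cannot be derived. The text is compatible with anything from none to all.

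**Illustration of size**

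From the documents: N = 20 at most (Study Summary, Section 10.2). One man is 1/20 = 5 percentage points.

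Assumed, because the documents give none of these:

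- d, the PET-only rate if conventional imaging were independent of the PET: 0.10 to 0.30
- f, the share of men staged after the PET: 0 to 1
- q, the chance that PET knowledge turns a negative conventional result positive: 0.25 to 0.75

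Expected PET-only men = N × d × (1 − f × q). For example, 20 × 0.20 × (1 − 1 × 0.75) = 1.0.

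| d | f = 0 | f = 0.5 (q 0.25 to 0.75) | f = 1 (q 0.25 to 0.75) |
|---|---|---|---|
| 0.10 | 2.0 | 1.75 to 1.25 | 1.5 to 0.5 |
| 0.20 | 4.0 | 3.5 to 2.5 | 3.0 to 1.0 |
| 0.30 | 6.0 | 5.25 to 3.75 | 4.5 to 1.5 |

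Exact (Clopper-Pearson) 95% intervals are 5.7% to 43.7% for 4 of 20 and 0.1% to 24.9% for 1 of 20. They overlap widely, so the counts alone would not reveal the distortion; scan dates would at least show which comparisons are exposed to it.

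The formula covers one mechanism. A late scan may instead show new disease, show treated disease that has regressed, or never be done. These act on other cells or in other directions.

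**The case against.** A reader might infer that the entry rules put most conventional imaging after the PET and that the comparator is therefore PET-informed. The documents do not support either statement:

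- Section 5.4 marks CT or MRI at screening, and Section 5.1 allows screening procedures up to 3 months before registration. That mark might mean only the mp-MRI; the text does not settle it.
- Section 4.5 does not say that risk group needs a biopsy, and Section 4.3 allows for surgery without one. Only bone scintigraphy is expressly tied to grade.
- The follow-up mark for CT/MRI has another documented use: post-treatment imaging to check regression.
- The statement in Section 7.3 concerns unblinding procedures and does not address image reading. No section says that those who report conventional scans see the PET.
- This is a secondary objective in a descriptive pilot. No error rate or decision rule depends on it.

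All of this stands and limits the claim to an unknown share and a possible effect. It does not remove the gap. Nothing in Section 10.3 separates scans reported before the PET from later ones, or comparator scans from confirmation scans. Being descriptive does not help either, because the PET-only and concordant percentages are themselves the result.

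**Conclusion.** The concern holds in limited form. The entry and staging rules make it likely that some conventional imaging is obtained after the PET, and possible that it is ordered or read with the PET known. Section 10.3 pools all of it. The PET-only and concordant cells can therefore be distorted.

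PET-aware imaging alone would shrink the PET-only cell. Under the assumed d of 0.20, it would fall from 4 of 20 to between 3 and 1 if all men were staged after the PET. Those figures rest on assumed d, f and q and are not estimates for this trial. The net direction and size cannot be derived from the documents. The issue affects how the secondary result is interpreted, and correcting it is a cheap improvement.

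**What to change.** 1. On the REDCap case report form, add the order date and report date of each conventional scan, relative to release of the PET result.
2. In Section 10.3, base the main table for Objective 2.2.1 on pre-treatment conventional imaging reported before that release. Include extraprostatic findings from the qualifying mp-MRI report where its coverage allows. The protocol does not state that coverage, so check it against the actual reports.
3. Tabulate imaging ordered or reported after release separately, labelled PET-informed. Use it to confirm PET sites and not as the main comparator.
4. Report the number of men with no pre-PET comparator.

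The cost is two date fields per scan and a few sentences in Section 10.3, with no new scan, reader or patient. The drawback is fewer comparisons in the main table, possibly many fewer for bone scintigraphy and non-pelvic sites. A masked re-read of later scans is not relied on here: the only study readers the protocol names are the two PET/CT readers, who may already have read the same man's PET.

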## 2.4 Endpoints

The primary endpoint is to determine per lesion sensitivity of  $^{68}\text{Ga}$  PSMA-11 for the detection of prostatic lesions in patients with elevated PSA and abnormal mp-MRI of the prostate (as defined as at least one lesion with PI-RADS v2.1 score 5 with any PSA or score 4 and PSA  $\geq 10$  ng/mL). A second endpoint will be to determine per person sensitivity of  $^{68}\text{Ga}$  PSMA-11 for the detection of metastatic disease, compared to standard of care imaging.

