Because of the small number of subjects, descriptive statistics will be used, such as percentage of times a focus of uptake in the prostate can be seen on the PET/CT and whether this focus corresponds to any detectable abnormality on review of mp-MRI of the prostate. With regard to lesions outside the prostate, comparison will be made with the results from the  $^{68}\text{Ga}$  PSMA-11 scan and possible lesions seen on conventional imaging, such as pelvic CT or MRI or bone scintigraphy.

If possible, biopsy confirmation of sites of abnormal focal  $^{68}\text{Ga}$  PSMA-11 uptake will be obtained per standard of care. If patient undergoes surgery without biopsy, findings of imaging will be correlated with whole mount pathology (WMP) of the resected gland with final pathology on the surgical specimen. For surgical patients, customized molds will be created based on MRI data to optimize co-registration of cross-sectional imaging and pathology data, as previously reported by our group [17]. If a patient undergoes radiation therapy or other ablation treatment without biopsy, post treatment conventional imaging will be performed and results will be compared for regression in size

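### For extraprostatic PET sites that cannot be biopsied, size regression is the only truth test named, and it cannot resolve some of the PET-only sites that objective 2.2.1 is about

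*Combined protocol and SAP*

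**What the plan says.** Objective 2.2.1 asks whether PET/CT "can detect additional sites of metastatic disease at staging in comparison to standard of care imaging". Section 10.3 gives those sites their own category in the comparison with conventional imaging: "uptake seen on PET/CT but normal on pelvic CT/MR/BS". The matching endpoint in section 2.4 is the "per person sensitivity of" the tracer for metastatic disease. Section 10.3 adds per-site sensitivity and false positives, laid out in a two-by-two table.

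On how a site is shown to be metastatic, section 10.3 starts with histology: where possible, biopsy confirmation of abnormal "uptake outside the prostate gland will be obtained". The fallback has a stated trigger, "If biopsy is not possible due to position or size of suspected lesion", and a stated test: "post treatment conventional imaging will be performed and results will be compared for regression in size". Section 4.3 gives a similar fallback with a different trigger: "If a patient undergoes radiation therapy or other ablation treatment without biopsy".

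Neither section says which scan supplies the baseline size, how much shrinkage counts, or when it is measured. Neither covers a site that has no measurable correlate, grows, first appears later, stays stable or is never treated. No indeterminate outcome is provided for.

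**The concern.** The fallback receives lesions that are too small or too awkwardly placed to biopsy. Section 1.1 says of CT and MRI of the pelvis that they "lack sensitivity as they are dependent upon size criteria and may not detect disease in smaller nodes". The truth test for the smallest sites therefore rests on the property that the protocol names as the weakness of the comparator.

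The rule also looks in one direction only. A PET-only site that later enlarges or becomes visible on CT is strong non-histological evidence of metastasis, yet it is not regression and so is not confirmed.

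At stake is whether the per-site figures can show that the extra PET sites are disease. Section 10.2 says that the pilot's data are meant to support a larger study, so a distortion here would carry into its planning.

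**Working it through.** The plan states no figure that bears on this point, so there is none to reproduce. The check has two parts.

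**1. Tracing an unbiopsied, PET-positive, conventionally normal site through the text**

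- *Normal-sized node visible on the study CT.* Section 4.2 acquires CT from skull to feet, and section 4.3 measures suspicious nodes in the short axis. A baseline can exist. If the node is treated and shrinks, the rule confirms it.
- *Site with no measurable correlate, for example a bone focus not seen on CT.* There is no size to regress, so the rule cannot confirm it.
- *Site that grows or newly appears on follow-up imaging.* This is not regression, so the rule cannot confirm it.
- *Site with no post-treatment scan, including one never treated.* The rule cannot be applied.

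Section 5.3 collects pathology, laboratory values and imaging for 2 years in order to correlate them with the scan. Section 10.3 does not make them part of the reference standard. The table in section 5.4 lists follow-up CT or MRI without timing and does not list bone scintigraphy.

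**2. What unresolved sites do to the reported figures (illustration; every count is assumed)**

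Let a = 6 true sites positive on both PET and conventional imaging, c = 2 true sites seen only on conventional imaging, and b = 2, 4 or 6 PET-only sites, all truly metastatic, of which v are verified.

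- Per-site sensitivity = (a + v) / (a + v + c). An unverified site adds nothing to this ratio, whether it is dropped or called a false positive.
- False-positive share of PET-positive sites, if unverified sites are counted as false positives = (b − v) / (a + b). If they are dropped, the share is 0.

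| b | Sensitivity, v = 0 | Sensitivity, v = b | False-positive share, v = 0, counted | True share |
|---|---|---|---|---|
| 2 | 6/8 = 0.75 | 8/10 = 0.80 | 2/8 = 25% | 0% |
| 4 | 6/8 = 0.75 | 10/12 = 0.83 | 4/10 = 40% | 0% |
| 6 | 6/8 = 0.75 | 12/14 = 0.86 | 6/12 = 50% | 0% |

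With half of the PET-only sites verified (v = b/2), sensitivity is 7/9 = 0.78, 8/10 = 0.80 and 9/11 = 0.82. The counted false-positive share is 1/8 = 12.5%, 2/10 = 20% and 3/12 = 25%.

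The table shows direction only, because its size follows from the assumed counts. It also assumes that every PET-only site is metastatic. If some are benign, dropping them would hide real false positives, which is a further reason to show unresolved sites openly.

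**The case against.** The strongest reply is that the gap is narrow, and most of that reply stands.

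- A reader might infer that PET-only sites have no conventional baseline. The documents do not support this. A node called normal by size can still be measured: every study scan includes CT, short-axis measurement is planned, and CT or MRI is listed at screening and follow-up. Section 10.3 names no baseline scan, so it does not exclude the study CT.
- A reader might infer that PET-only sites cannot be confirmed at all. Biopsy comes first, and the 2-year follow-up could settle others if section 10.3 used it.
- The count of PET-positive, conventionally normal sites needs no truth test, so part of objective 2.2.1 is untouched. The per-person endpoint is also less exposed, since a man with another confirmed site keeps his status.
- A reader might extend the point to the prostate, because section 4.3 applies size regression after radiation or ablation. There, section 10.3 names pathology as the reference, and criterion 3.1.4 requires a scheduled biopsy or prostatectomy. The sentence does not claim to verify individual prostate foci.
- This is a descriptive pilot of up to 20 men with no hypothesis test.

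The last point does not dispose of the matter. The plan commits to reporting per-site sensitivity and false positives, and those figures need a reference standard that can classify the sites or say openly that it cannot.

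**Conclusion.** The concern holds for a limited group: unbiopsied extraprostatic sites that have no measurable correlate, have no post-treatment scan, or change in a way other than regression. Followed as written, the rule leaves a true metastasis in that group unconfirmed, and the two-by-two table then forces it to be counted as a false positive or dropped. For truly metastatic sites both routes lower per-site sensitivity relative to full verification, and counting them also raises false positives. The loss falls on the sites that would show PET's added value.

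The size cannot be derived from the documents. They give no expected number of extraprostatic sites, PET-only share, biopsy rate or proportion without a correlate, and do not say how unresolved sites are handled. The percentages in the illustration should not be read as an estimate of the bias. This is a correctable weakness in the per-site analysis and does not invalidate the study.

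**What to change.** In sections 10.3 and 4.3, replace the size-regression test with a prespecified composite reference standard built from the 2-year follow-up data:

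- **Confirmed:** positive histology; or a correlate that shrinks after that site was treated; or a correlate that grows or newly appears on follow-up imaging.
- **Not metastatic:** negative histology or an established benign explanation.
- **Not verifiable:** everything else, including no measurable correlate, no follow-up scan, and stable or discordant change.

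Take baseline size from the CT of the study PET/CT, and state in advance what counts as a measurable correlate and as a change in size. Report the main per-site table on verified sites and list the not-verifiable sites in a separate row. Beside it, give the range obtained by counting them all as true positives and then all as false positives. With the assumed counts above and b = 4, none verified, that range would be a sensitivity of 0.75 to 0.83 and a false-positive share of 0% to 40%.

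The change costs protocol wording and one extra row. It should require no scans beyond those already planned. The drawback is a smaller verified denominator: some sites will be reported openly as unresolved.

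### Section 10.3 plans no analysis of the per-person metastatic sensitivity named in Section 2.4, and its per-site PET/CT sensitivity has no stated route to confirmed false negatives

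*Combined protocol and SAP*

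**What the plan says.** **Endpoint.** Section 2.4 states: "A second endpoint will be to determine per person sensitivity of" the tracer "for the detection of metastatic disease, compared to standard of care imaging". The unit is the man and the comparator is standard imaging.

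**Objective.** Section 2.2 asks whether PET/CT "can detect additional sites of metastatic disease at staging in comparison to standard of care imaging". The unit there is the site.

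**Analysis.** For lesions outside the prostate, Section 10.3 plans two things. The first is a table of PET/CT against pelvic CT, MRI or bone scan, given as percentages of incidences (a unit it does not define): concordant, PET-only, and "no uptake on PET/CT but lesion seen on pelvic CT/MR/BS". No reference standard enters this table. The second is the accuracy result: "The per-site diagnostic performance of PET/CT (sensitivity and false positives) will be reported".

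**Confirmation.** In 10.3, biopsy where possible is attached to abnormal focal "PSMA-11 uptake outside the prostate gland will be obtained". If biopsy is not possible, "post treatment conventional imaging will be performed and results will be compared for regression in size". Section 4.3 has a matching biopsy sentence ("If possible, biopsy confirmation of sites of abnormal focal" uptake). It then adds two rules that apply by patient: correlation with surgical pathology for men who have surgery without biopsy, and post-treatment conventional imaging for men who have radiation or ablation without biopsy. Section 5.3 provides two years of clinical, pathology, laboratory and imaging follow-up, and the Section 5.4 table marks pathology review and CT or MRI at follow-up.

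**The concern.** A sensitivity needs a unit, a denominator of truly diseased units, and a way to find the diseased units that the test missed. For the prostate, 10.3 supplies these: the unit is the lesion, as in the primary endpoint, and pathology is named as the reference standard. For metastatic disease the unit does not match 2.4, standard imaging gets no sensitivity, and there is no stated route by which a PET-negative site or man becomes a confirmed false negative.

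Two consequences follow. The per-person endpoint has no specified analysis, and the per-site figure cannot stand in for it. The per-site figure also depends on an unstated rule for lesions seen only on conventional imaging, so two analysts could report different sensitivities from the same data. Section 10.2 says the results are meant to support a larger study, so an ill-defined sensitivity would be carried forward.

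**Working it through.** The plan states no sensitivity, prevalence, power or precision figure, and the sample size of up to 20 has no formula behind it, so there is no figure to reproduce. All counts and rates below are illustrative assumptions.

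**1. Endpoint against analysis**

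| Element | Section 2.4 | Section 10.3, outside the prostate |
|---|---|---|
| Unit | person | site (accuracy); undefined (concordance) |
| PET/CT sensitivity | yes | yes, per site |
| Standard imaging | comparator | concordance percentages only |
| Reference for PET-negative units | not stated | not stated |

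**2. Unit.** Assume four men with 10, 1, 1 and 1 metastatic sites, where PET finds all 10 in the first man and none in the others. Per site: 10/13 = 76.9%. Per person: 1/4 = 25%.

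**3. Conventional-only lesions left out (verification bias).** Let Se be the true sensitivity and v the share of PET-negative diseased sites that are verified, with all PET-positive diseased sites verified. Apparent sensitivity = Se / (Se + (1 − Se)·v).

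| True Se | v = 0 | v = 10% | v = 25% | v = 50% | v = 100% |
|---|---|---|---|---|---|
| 40% | 100% | 87.0% | 72.7% | 57.1% | 40% |
| 60% | 100% | 93.8% | 85.7% | 75.0% | 60% |
| 80% | 100% | 97.6% | 94.1% | 88.9% | 80% |

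The direction is upward. The v = 0 column is an extreme bound, not a forecast.

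**4. Conventional-only lesions counted unverified (reference misclassification).** Let TP be confirmed PET-positive sites, K real conventional-only lesions, B benign conventional-only lesions, and M true sites negative on both tests.

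- Reported = TP / (TP + K + B). True = TP / (TP + K + M).
- So reported exceeds true if B < M, and falls below it if B > M.
- With TP = 8 and K + B = 4, reported = 8/12 = 66.7%.
- If K = 4, B = 0, M = 2: true = 8/14 = 57.1%, so the report is too high.
- If K = 2, B = 2, M = 0: true = 8/10 = 80.0%, so the report is too low.

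The documents give neither B nor M. Section 1.1 notes that bone scintigraphy may lack specificity, so B cannot be assumed to be zero.

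**5. Precision of a per-person result.** At assumed metastatic prevalences of 10%, 20%, 30% and 40%, 20 men give 2, 4, 6 and 8 men with metastases. If PET/CT finds all of them, the exact (Clopper-Pearson) 95% lower limits are 15.8%, 39.8%, 54.1% and 63.1%. For 6 of 8 the interval is 34.9% to 96.8%.

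**6. Effect of indeterminate men.** Assume 4 confirmed PET-positive men. If 3 PET-negative men are indeterminate, sensitivity runs from 4/4 = 100% (exact interval 39.8% to 100%) to 4/7 = 57.1% (18.4% to 90.1%). If all 16 other men are indeterminate, it runs from 4/4 = 100% to 4/20 = 20%.

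**The case against.** The strongest reply is that this is a descriptive pilot of up to 20 men and a secondary endpoint. The concordance table and the per-site result serve the objective in 2.2 directly. On this view the outlier is one phrase in 2.4, and amending 2.4 would remove the unit conflict. Per-person results could also be derived from site data, and a comparison with standard imaging need not mean a separate sensitivity for it.

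Part of this stands. The concordance table and the counts of confirmed PET-positive sites remain usable, and realigning 2.4 would settle the unit. It would not settle the reference: the per-site sensitivity would still have no rule for PET-negative lesions. Pilot status excuses the lack of power and tests, but not an undefined denominator. Reading the comparison in 2.4 as one of sensitivities is the natural reading, though not the only possible one.

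Four stronger readings are tempting, and the documents do not support them.

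- *Only PET-positive sites can ever be verified.* The surgery and radiation/ablation rules in 4.3 apply by patient, the follow-up in 5.3 and 5.4 is not limited to PET-positive men, and the suspected lesion in the 10.3 fallback can be read more widely. Verification of PET-negative disease is unlinked and unspecified, not excluded.
- *The trial will report 100%.* That requires an empty false-negative cell in a table meant to show sensitivity, so it is only a bound.
- *The bias is always upward.* It is upward if conventional-only lesions are left out. If they are counted unverified, step 4 shows that it can go either way.
- *Many men will have no staging scan beyond the mp-MRI.* Section 4.5 calls cross-sectional imaging standard of care in unfavorable intermediate or high risk disease but does not say that other men go without. The screening CT or MRI entry in 5.4 does not settle the matter.

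**Conclusion.** The concern holds. Followed as written, 10.3 does not deliver the second endpoint of 2.4: it plans no per-person sensitivity and no sensitivity for standard imaging. The per-site PET/CT sensitivity that it does plan has no stated route to confirmed false negatives. It is open to upward verification bias if conventional-only lesions are left out, and to misclassification in either direction if they are counted unverified.

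The documents give no figures from which to size either effect. The illustrations show only that the choice of unit and the unstated rule can move the result by tens of percentage points. They rest on assumed counts, sensitivities and verification rates, with all PET-positive diseased sites taken as confirmed. This should be fixed before analysis. It does not invalidate the concordance table or the prostate analysis.

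**What to change.** Change the wording of Section 10.3:

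1. Add a paired per-person table (any metastasis, yes or no) for PET/CT and for standard imaging, with counts and exact 95% intervals. Keep the per-site table for the objective in 2.2.
2. Judge both tests against one composite reference applied whatever the PET result: histology where available, otherwise the imaging and clinical follow-up already planned in 4.3, 5.3 and 5.4. Count a conventional-only lesion as a PET false negative only when that reference confirms it. Class unresolved sites and men as indeterminate, and show results with them all positive and all negative.
3. Set in advance the criterion for reporting sensitivity, for example a minimum share of PET-negative men with a reference result. If it is not met, report detection rate, positive predictive value and concordance, and do not call the result sensitivity.

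**Cost.** No added biopsy or scan; the change is to the analysis text. The downsides should be stated in the plan. Reported sensitivity may be lower. Many men could be indeterminate, because the study duration in the Study Summary and the follow-up in 4.6 are both two years, so later enrollees may have short follow-up. Follow-up imaging may use the same modalities being compared, which favors those modalities in the reference. Intervals stay wide with up to 20 men.
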